# 6.2 Management of losses to follow-up

If a participant is being lost to follow-up (for instance, not showing up to their study visits), the following procedures will be performed:

- Participant will be contacted three times and efforts will be clearly documented. Contacts may be done either by telephone, electronically, or mail correspondence;
- ii) Obituaries will be verified online;

iii) If unsuccessful after three attempts, a registered letter will be sent to the participant's address requesting the participant to sign for the letter to attempt to confirm survival status. If no response, efforts will be clearly documented, status as lost to follow-up.

Participants who voluntarily withdraw early from the study will be asked about permission to have their data used (as detailed in section 6.1).

### 6.3 Premature termination or suspension of trial

The study may be suspended or prematurely terminated if there is sufficient reasonable cause. If the study is prematurely terminated or suspended, it will be promptly reported to the REB and the reason(s) will be provided.

### 7. Study treatments

Participants will be randomized 2:1 to self-management (intervention) or usual care (comparator). The current standard of care for patients with IgA nephropathy attending the Glomerulonephritis Clinic is to measure their blood pressure at scheduled clinic visits and make treatment decisions based on those values. Clinical guidelines recommend RAAS inhibitors as first-line therapy. Patients not requiring immunosuppression treatment are typically followed in the clinic every 4 to 6 months. Participants in the intervention and control group will be assessed in the clinic at baseline, at 3 months and at 6 months. In both groups, the dose of RAAS inhibitor will be progressively increased to achieve a systolic BP <120 mmHg. The use of other antihypertensive medications will be permitted in both groups at the discretion of the treating physician after the dose of RAAS inhibitor has first been maximized. For patients receiving other (non-RAAS inhibitor) antihypertensive therapy at the time of recruitment, these medications will be replaced by a RAAS inhibitor at study entry. As such, they will be receiving care at a level at or above the current standard of care. Patients in the intervention group will additionally measure their blood pressure at home and follow the algorithm as described below.

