	
 
Proteinuria > 0.5 g/day quantified from 24-hour urine collection or urine protein:creatinine ratio >50 mg/mmol or urine albumin:creatinine ratio >30 mg/mmol
 
Clinic systolic BP >130 mmHg or diastolic BP >85 mmHg (automated office BP measurement)
 
Willing to self-manage BP
 

Exclusion criteria	Any of the following:
	Currently receiving immunosuppression or in need of urgent start immunosuppression (e.g., rapidly progressive glomerulonephritis or nephrotic syndrome)
	
 
Kidney failure defined by the need for dialysis, kidney transplantation or eGFR <15 mL/min
 

	Recent (within 3 months) history of acute myocardial infarction or stroke
	Heart failure with reduced ejection fraction
	Concomitant diabetic nephropathy on kidney biopsy
	Pregnancy (or actively planning a pregnancy) or breastfeeding
	Life expectancy <12 months
	Allergy or intolerance to both an angiotensin converting enzyme
	inhibitor and angiotensin II receptor blocker
	Severe hypertension (>180/100 mmHg)
Treatments	Intervention arm (study treatment)
	Self-management of BP including self-monitoring of home BP values and self-titration of medications according to a pre-specified individualized
	treatment plan
	Control arm
	Usual management of BP and anti-hypertensive therapy by a physician at regularly scheduled clinic visits
Sample size pilot trial	Target recruitment: 25 patients over 2 years across three sites (The Ottawa Hospital Glomerulonephritis Clinic and the Glomerulonephritis Clinic in Vancouver General Hospital and St. Paul's Hospital, Vancouver)
	Justification: The target sample size is primarily based on the incidence of
	IgA nephropathy and the anticipated recruitment rate from the clinic. We
	will seek to recruit newly diagnosed patients but will also include prevalent
	patients at each site. The target sample size should be sufficient to address
	practical questions regarding the feasibility of conducting a larger clinical
	trial with respect to recruitment, ease of implementation of the intervention,
	and collection of efficacy and safety outcomes. The total sample size of 25
	participants is further supported by a sample size calculation for the
	participanto is further supported by a sample size calculation for the

	feasibility metric of retention of participants in the trial. The progression criterion for this outcome is 80%. Assuming 90% of participants complete

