# 1.3 How should supportive care be delivered?

Despite the recognized benefits of supportive therapy, there is no uniform strategy that defines optimal supportive care. This can be readily seen from two recent randomized controlled trials (RCTs) of immunosuppression for IgAN, which entered participants who met inclusion criteria in a run-in phase with the intent of maximizing supportive care prior to randomization. The STOP-IgAN trial (N=309) followed patients monthly for 6 months and titrated the dose of RAAS inhibitor to target BP <125/75 mmHg at each visit, along with offering lipid-lowering therapy and counseling about a low-sodium diet and smoking cessation, while the TESTING trial (N=523) had a run-in phase of 4 to 12 weeks (for a total of two to three study visits) to ensure that all participants were on a RAAS inhibitor for 3 months prior to randomization but had no BP target. Despite the different approaches used, 34% (n=106) of patients who completed the run-in period in STOP-IgAN achieved a response (reduction in proteinuria to <0.75 g/day), and 24.5% (n=128) of patients in TESTING experienced a reduction in proteinuria to the extent that they no longer met the inclusion criteria for randomization.8 These two RCTs show that a substantial proportion of patients can achieve at least a short-term reduction in proteinuria with supportive therapy alone. However, there remain some important knowledge and care gaps. It is unclear whether the need for frequent in-person visits, beyond what is typical in routine care, would be feasible in most settings, as well as potentially placing additional burden on patients. Trial participants have not been randomized during the run-in phase of contemporary RCTs and no specific supportive care interventions have been formally tested, including the systolic BP target of 120 mmHg suggested by international guidelines.

The current standard of care for BP treatment is according to automated office BP readings at in-person clinic visits. Among 91 patients with incident IgAN diagnosed on a kidney biopsy between January 2020 and December 2022 at The Ottawa Hospital, 58% of patients had a systolic BP >120 mmHg and 38% of patients were receiving sub-

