maximal doses of a RAAS inhibitor at six months' follow-up ([name], personal communication). Studies of ambulatory BP monitoring in patients with glomerulonephritis have shown a high prevalence of masked hypertension, nocturnal hypertension, and non-dipping status, 15,16 highlighting the limitations of relying solely on clinic BP readings. In one cross-sectional study, systolic BP from ambulatory monitoring had a stronger correlation with both kidney function and albuminuria compared to systolic BP from clinic readings. In a small prospective study, patients with glomerulonephritis who had normal clinic BP and preserved kidney function were found to have higher ambulatory BP values compared to matched controls, along with early evidence of left ventricular hypertrophy. Targeting ambulatory BP has not been systematically evaluated in patients with IgAN and could provide opportunities for earlier intensification of RAAS inhibitor therapy, better overall BP control and improvements in proteinuria.

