### 5.1 Inclusion criteria

- Adult patients aged ≥18 years who provide written informed consent.
- Biopsy-confirmed diagnosis of IgAN.
- Proteinuria > 0.5 g/day quantified from 24-hour urine collection or urine protein:creatinine ratio >50 mg/mmol or urine albumin:creatinine ratio >30 mg/mmol.
- Clinic systolic BP >130 mmHg or diastolic BP >85 mmHg (automated office BP measurement)
- Willing to self-manage BP

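### Section 7's rule replacing non-RAAS antihypertensives at entry has no condition on current RAAS inhibitor use, so it conflicts with the sentence before it for patients already on a maximized RAAS inhibitor plus another agent

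*Protocol*

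**What the plan says.** Section 7 (Study treatments) sets the drug rules for both arms in consecutive sentences. The RAAS inhibitor dose is raised step by step towards a systolic pressure below 120 mmHg. Other antihypertensives are "permitted in both groups at the discretion of the treating physician after the dose of RAAS inhibitor has first been maximized". For anyone taking a non-RAAS agent when recruited, "these medications will be replaced by a RAAS inhibitor at study entry". The section then draws the conclusion that "they will be receiving care at a level at or above the current standard of care".

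Three other places determine who meets these rules:

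- The sample size row of the Study synopsis says the team "will seek to recruit newly diagnosed patients but will also include prevalent" patients at each site.
- Section 5.1 sets blood pressure entry by clinic reading alone, above 130 mmHg systolic or 85 mmHg diastolic.
- Section 5.2 excludes severe hypertension above 180/100 mmHg and patients who cannot take either class of RAAS inhibitor. It has no criterion on RAAS inhibitor dose or on additional agents.

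**The concern.** The replacement sentence is mandatory, and its only trigger is that a non-RAAS drug is being taken. It does not ask whether the participant already has a RAAS inhibitor at full dose. Prevalent patients can enter, and in such patients a maximized RAAS inhibitor with a second drug is an ordinary regimen. If that patient's pressure is still above the entry limit, nothing is left to substitute. Following the sentence as written would leave the participant with less treatment than before enrolment.

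Two things are at stake. The first is safety, for any participant whose effective second drug is stopped at entry. The second is uniform treatment: one site may follow the replacement sentence and another the permissive one, so the same patient could be handled in two ways within one protocol.

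**Working it through.** There is no figure to reproduce. The check is whether the two sentences in section 7 can both be followed for each kind of patient that sections 5.1 and 5.2 admit. Call the permissive sentence rule 1 and the replacement sentence rule 2.

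| Regimen at recruitment | Rule 1 (other agents after maximization) | Rule 2 (replace other agents at entry) | Compatible? |
|---|---|---|---|
| (a) No RAAS inhibitor, another agent | Not yet permitted | Other agent out, RAAS inhibitor in | Yes: switch, titrate, add back if needed |
| (b) RAAS inhibitor below maximum, another agent | Not yet permitted | Other agent out, RAAS inhibitor raised | Yes, in sequence, although the participant already takes the drug named as the replacement |
| (c) RAAS inhibitor maximized, another agent | Permitted, at physician discretion | Other agent out; the RAAS inhibitor cannot go higher | No |

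**Is (c) eligible?** Yes. Nothing in 5.1 or 5.2 refers to RAAS inhibitor dose or to a second agent, and prevalent patients are recruited. By the entry criterion, every such participant has a clinic pressure above 130 mmHg systolic or 85 mmHg diastolic.

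**Does other text narrow rule 2?** Not expressly. Section 7.1.2 leaves the drug and dose in the three-step plan to the physician, and the synopsis describes the control arm as usual physician management. Neither mentions the replacement at entry, and nothing states which sentence prevails.

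**Does a scheduled check follow the stop?** The 7 to 10 day check in section 9.1 measures creatinine and potassium. It is tied to starting a RAAS inhibitor or, under listed conditions, raising its dose. Neither happens in (c). Self-management participants have a practice week and monthly home readings (7.1.1). Control participants next have a scheduled measurement at week 12 (section 8, Visit 2).

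**Does it touch the pilot's conclusions?** No. Section 3.1 bases progression on recruitment and retention. Section 3.2 makes the blood pressure outcomes exploratory. Rule 2 is the same in both arms.

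**The case against.** The best defence is that replacing one drug with another presupposes that the second can be brought in. Where the RAAS inhibitor is already at full dose, the sentence arguably has no application, and reading it as a bare stop adds an instruction. On this view section 7 simply moves patients treated with something else onto first-line therapy. The physician has discretion under rule 1 in both arms, under 7.1.2 in the self-management arm, and through usual management in the control arm.

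Much of this stands. The authors probably meant it that way, and a sensible physician would probably keep the second drug, so harm is unlikely. What remains is that the sentence does not say so. Its wording is mandatory and covers every participant on a non-RAAS agent. Keeping the drug departs from that wording, and section 10.3 requires departures to be documented and reported.

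A reader might infer three stronger points, none of which the Protocol supports:

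- **That many participants are affected.** Section 1.3 reports that, among 91 incident Ottawa patients at six months, 58% had systolic pressure above 120 mmHg and 38% were on sub-maximal RAAS inhibitor doses. The remaining 62% are not divided into full dose and no RAAS inhibitor, second-agent use is not given, and 120 mmHg is not the entry limit. No count for group (c) follows.
- **That controls are left too long without a blood pressure check.** The Protocol says: "Patients not requiring immunosuppression treatment are typically followed in the clinic every 4 to 6 months". At 30.4 days per month that is 4 × 30.4 / 7 = 17.4 weeks to 6 × 30.4 / 7 = 26.1 weeks. Week 12 is earlier than either. The interval is not the defect; an unneeded drug stop at its start would be.
- **That the rule biases the comparison between arms.** It is worded identically for both.

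**Conclusion.** The point holds as a minor safety and consistency defect confined to one subgroup: eligible participants already on a maximized or maximally tolerated RAAS inhibitor plus another antihypertensive. For them the two sentences cannot both be followed, and literal compliance with the replacement sentence sits badly with the claim about standard of care that comes next. For everyone else the sentences are compatible.

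The size is unknown and may be zero. The conclusion assumes only that such a patient can be enrolled, which the eligibility criteria allow. It does not assume that any site would actually stop the drug. No pilot endpoint or progression criterion is affected. It merits correction because the conflict is in the text and a short edit removes it.

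**What to change.** Limit the replacement sentence in section 7, for example:

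> If a participant takes a non-RAAS antihypertensive at recruitment and their RAAS inhibitor is absent or not yet maximized, a RAAS inhibitor will be started, or its dose increased, in place of that agent when they enter the study. Participants whose RAAS inhibitor is already maximized, or at the highest tolerated dose, may continue their other agents if the treating physician so decides.

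Starting or increasing the RAAS inhibitor also makes the instruction sensible for group (b). Naming the highest tolerated dose matters because section 7 speaks only of maximization, while section 1.5 gives the maximally tolerated dose as the recommendation for these patients.

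The cost is one condition and one added sentence, with the usual ethics board review of an amendment. No participants, visits, blood pressure checks or case report form fields are added.

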### 7.1 Intervention

Participants randomized to self-management will receive training in home BP measurement and adjustment of anti-hypertensive medications according to a prespecified plan.

### 7.1.1 Home BP measurement

Participants will be provided with a home BP monitor with an appropriately sized cuff, and will receive a 30-minute in-person teaching session from a research nurse (or research coordinator) about how to accurately measure their BP at home. Written instructions will also be provided (these are already available in the clinic in both English and French). Participants will have a practice week of BP measurement to ensure that the training was successful and to identify participants who would benefit from additional training. Participants will be asked to measure their BP twice daily (morning and evening) for 7 consecutive days at the beginning of each month (measurement week). They will be advised to measure their BP in a seated position with their arm supported such that the middle of the cuff is at the level of the heart. Each measurement will include 3 values taken 1 minute apart after 5 minutes of rest. The average of values 2 and 3 will be recorded as the BP for that measurement. A complete week of measurements will therefore encompass 14 BP values (7 morning and 7 evening values). An instruction sheet will be provided to each participant to explain what should be done based on their BP values. Very low readings (<100 mmHg systolic) or very high readings (>180 mmHg systolic) that persist after repeating another set of 3 measurements will prompt a phone call to the clinic staff for advice.

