# 3. Outcomes

# 3.1 Primary outcome

The primary outcome of the pilot trial will be feasibility defined as achieving target threshold for both recruitment and study completion. The study protocol will be revised based on adherence metrics and participant feedback as detailed below:

- 1. The probability of successful recruitment will be calculated as the percentage of eligible participants who are randomized. A threshold of >50% will be required for progression to a full-scale trial.
- 2. The probability of retention will be calculated as the percentage of randomized patients who complete the study. A threshold of >80% will be sought for progression to a full-scale trial.
- 3. Adherence to the self-management protocol will be quantified for each patient in the intervention group using the median number of recorded home BP readings per measurement week. Adherence will be further explored from participant feedback in longitudinal diary entries and a semi-structured interview. Fidelity of the intervention will also be explored retrospectively by comparing the submitted BP readings to the BP readings downloaded from the machine at the end of the study period. There is no progression criterion for adherence but the study protocol for a future full-scale trial will be refined based on these factors.

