#### 5.2 Exclusion criteria

- Currently receiving immunosuppression or in need of urgent start immunosuppression (e.g., rapidly progressive glomerulonephritis or nephrotic syndrome).
- Kidney failure defined by the need for dialysis, kidney transplantation or eGFR
   <15 mL/min.

- Recent (within 3 months) history of acute myocardial infarction or stroke.
- Heart failure with reduced ejection fraction.
- Concomitant diabetic nephropathy on kidney biopsy.
- Pregnancy (or actively planning a pregnancy) or breastfeeding.
- Life expectancy <12 months.
- Allergy or intolerance to both an angiotensin converting enzyme inhibitor and angiotensin II receptor blocker.
- Severe hypertension requiring urgent treatment (>180/100 mmHg).

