# 7.1.2 Adjusting anti-hypertensive therapy

Within the same encounter, a second 30-minute teaching session will be delivered to participants regarding the treatment algorithm for titration of anti-hypertensive medications. Each participant will have an individualized three-step treatment plan that is developed with their physician, and which is based on their recorded home BP values during the measurement week of each month. The choice of anti-hypertensive agent and dose is at the physician's discretion. Participants who record 50% or more values above target during their measurement week will move to the next step of their

treatment plan (either increasing their home dose of RAAS inhibitor or contacting their physician for a new medication prescription). In this way, there is no requirement for an additional clinic encounter. Once the three steps have been completed, the participants will return to the clinic to create a new three-step plan. In consultation with our patient partners, we established that a minimum of 8 BP values during a measurement week (equivalent to 4 out of 7 measurement days) would be required in order for any medication changes to be made. If a participant is unable to complete the requisite number of BP measurements, they will be given an opportunity to repeat the set of BP measurements the following week (as opposed to waiting until the following month).

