# 9. Safety assessments

### 9.1 Potential risks to participants

Participants in the intervention arm could be at a higher risk of adverse events from more rapid escalation of their anti-hypertensive therapy. Serum creatinine and

potassium will be checked within 7 to 10 days of initiating a RAAS inhibitor. Laboratory tests will be rechecked within 7 to 10 days of increasing the dose of a RAAS inhibitor in the following situations: (i) previous serum potassium value ≥4.8 mmol/L; (ii) eGFR <30 mL/min; or (iii) physician discretion. Participants will be encouraged to contact the clinic staff outside of scheduled encounters if they develop symptoms indicative of low blood pressure (light-headedness, weakness). Sitting and standing BP will be measured at each study visit to look for evidence of orthostatic hypotension. Each participant will be provided with "sick day guidance" with respect to stopping their RAAS inhibitor during acute illness. Participants may feel apprehensive or overwhelmed about having to self-manage their blood pressure. The potential for participant burden has been a major focus for our team in development of this protocol. Our patient partners have provided feedback about each step of the process to mitigate this risk.

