# 9.3 Adverse event recording and reporting

The adverse event recording period will begin with entry into the study (day of randomization) and end on the last study visit approximately 26 weeks after randomization. All AEs will be recorded in the electronic CRF. Adverse events will be

captured by the site investigator or designee by inquiring about safety events since the last visit. Safety assessments may also be collected from participant report prior to the study visit by the patient contacting the research personnel, or by review of the clinical chart by the research personnel. Investigators have the primary responsibility for adverse event identification, documentation, grading, attribution of causality and reporting. AEs that are related to study treatment will be reported to the individual site's ethics board.

Local investigators will record the causality of the SAE in relation to the study treatment. Causality will be assessed as follows:

- Unrelated: There is not a reasonable possibility that the adverse event may have been caused by the study intervention.
- Possibly related: The adverse event may have been caused by the study intervention, however there is insufficient information to determine the likelihood of this possibility.
- Related: There is a reasonable possibility that the adverse event may have been caused by the study intervention.

When deciding about causal relationship, the investigator will consider whether the event may be the result of diseases or concomitant medications which typically can occur in this patient population such as: the natural progression of an existing disease, the development of a new and unrelated disease, or a known side effect of other concomitant therapies that the participant may be taking.

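### The home safety alert in Protocol 7.1.1 is systolic only, so a persistent very high home diastolic (for example 150/110) prompts no immediate call for advice

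*Protocol*

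**What the plan says.** Protocol 7.1.1 sets the readings that must prompt a phone call to clinic staff: "Very low readings (<100 mmHg systolic) or very high readings (>180 mmHg systolic) that persist after repeating another set of 3 measurements". Both limits are systolic. The protocol gives no diastolic limit for home readings.

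Diastolic pressure does count at entry. Section 5.1 accepts "Clinic systolic BP >130 mmHg or diastolic BP >85 mmHg (automated office BP measurement"), so a raised diastolic alone qualifies. Section 5.2 excludes "Severe hypertension requiring urgent treatment (>180/100 mmHg").

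The stated treatment target is systolic: "In both groups, the dose of RAAS inhibitor will be progressively increased to achieve a systolic BP <120 mmHg" (section 7). Under 7.1.2 a participant moves one step when at least half of the week's values are above target, with at least 8 values recorded. The step is "either increasing their home dose of RAAS inhibitor or contacting their physician for a new medication prescription". The lay summary (Methods) mentions only the second of these routes.

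Other routes to staff carry no blood pressure value:
- Section 9.1 encourages participants to "contact the clinic staff outside of scheduled encounters if they develop symptoms indicative of low blood pressure".
- Section 9.3 allows safety information to arrive "by the patient contacting the research personnel, or by review of the clinical chart by the research personnel".
- Section 3.1 describes a retrospective fidelity check, "comparing the submitted BP readings to the BP readings downloaded from the machine at the end of the study period". It does not say when staff look at submitted values during the trial.

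**The concern.** The alert is the only stated rule that takes a single confirmed home reading straight to a clinician. It has the 180 of section 5.2 but no counterpart to the 100. A participant at 150/110 can follow every instruction correctly and not be told to call. Prompt advice then depends on the participant phoning unasked, on someone noticing a submitted value, or on the next step or visit.

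What is at stake is the safety of the home instructions. Section 4.3 gives the intervention's acceptability and safety profile as the reason for 2:1 allocation, and instructions tested here would be expected to carry into the full-scale trial.

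**Working it through.** The plan gives no figure of its own on this point, so there is nothing to reproduce. The stated rules are applied to an example, and the size of the gap and of the fix is then bounded.

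**Inputs from the protocol.** Alert limits: systolic <100 and >180, confirmed by a repeat set (7.1.1). A full week is 14 values (7.1.1). Target: systolic <120 (section 7); 7.1.2 does not define its target, so it is read this way. Step rule: at least 50% of values above target (7.1.2). A week that is too incomplete may be repeated the following week (7.1.2). Size and allocation: 25 participants, 2:1 (12.1, 4.3).

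**Assumptions.** Within-person SD of 8 to 12 mmHg systolic and 6 to 10 mmHg diastolic; normal, independent readings. The documents give no such SDs, and independence is a simplification.

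**1. Rules applied to 150/110.** Systolic 150 is neither <100 nor >180, so there is no call. No rule tests the diastolic 110. Because 150 is above 120, the reading counts towards a step.

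**2. Does the systolic alert stand in for a diastolic one?** Per-reading chance p = 1 − Φ((limit − mean)/SD). Weekly chance of an alert is 1 − (1 − p)^14 if the repeat set always confirms, and 1 − (1 − p²)^14 if the repeat is independent.
- Limit 180, mean systolic 150, SD 8/10/12: p = 0.00009/0.0013/0.0062. Weekly chance 0.12/1.87/8.35% if always confirmed; at most about 0.05% if independent.
- Diastolic limit 100, mean 110, SD 6/8/10: p = 0.952/0.894/0.841. Weekly chance over 99.9% either way.
- Diastolic limit 110, mean 110: p = 0.5 at any SD. Weekly chance 1 − 0.5^14 = 99.99%, or 1 − 0.75^14 = 98.2% if independent.

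So the systolic alert is no substitute. A diastolic limit of either 100 or 110 would catch this participant.

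**3. What happens instead, and when.** At mean systolic 150, P(systolic >120) = 1 − Φ((120 − 150)/SD), which is at least 0.994 for SD 8 to 12. P(Binomial(14, p) ≥ 7) exceeds 99.9%, so a step is practically certain. It comes after the week ends: up to 7 days from a day-1 reading, or 7 + 7 = 14 days if the week is repeated. A confirmed systolic above 180 prompts a call without that wait.

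**4. When does no stated rule respond?** This needs systolic mostly below 120 with diastolic above 100, a pulse pressure under 120 − 100 = 20 mmHg. That is remote.

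**5. Extra calls from a diastolic alert.** Percentage of measurement weeks with a call, from independent repeat to always confirmed, using the same formulas:

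| Limit | Mean home diastolic | SD | p | Weeks with a call |
|---|---|---|---|---|
| 100 | 80 | 8 | 0.0062 | 0.05–8.35% |
| 100 | 90 | 8 | 0.1056 | 14.5–79.1% |
| 110 | 80 | 8 | 0.00009 | up to 0.12% |
| 110 | 90 | 8 | 0.0062 | 0.05–8.35% |

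The SD matters. At mean 90, SD 6 to 10 widens the range to 3–91% for limit 100 (p = 0.048 to 0.159) and to 0–28% for limit 110 (p = 0.0004 to 0.023).

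**6. Exposure.** 25 × 2/3 = 16.7 participants; 16.7 × 6 monthly weeks = 100 measurement weeks.

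**The case against.** The strongest reply is that 150/110 does get a response. The systolic target triggers a step in practically every such week, and one of the two stated routes is contact with the physician; the lay summary names only that route. This stands. A reader might infer that such a participant is left without any response, and the documents do not support that. What is missing is the immediate call, and 7.1.2 does allow the step to be a home dose increase with no contact.

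A reader might also infer that 7.1.1 contradicts 5.2, or that the protocol itself classes 150/110 as needing urgent treatment. Neither follows. Section 5.2 is an enrolment exclusion, and its slash does not say whether both limits or either one must be exceeded. If both, 150/110 is not excluded. The section shows that the sponsor thought diastolic pressure relevant, but it does not fix a home limit of 100. Likewise, entry on diastolic >85 does not imply home values above 100.

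The systolic focus is consistent across target, primary efficacy outcome and full-trial power. That explains the rule, but a safety alert need not be limited to the efficacy variable.

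The instruction sheet and individual plans are not shown and could carry a diastolic limit. If they do, 7.1.1 should state it, because it sets out the alert explicitly and only in systolic terms.

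Intervention participants keep the same clinic visits as controls and add home readings, so the gap does not leave them less observed than controls. Participant burden is a stated concern, and a limit of 100 could generate many calls. Both points stand and bear on the choice of limit.

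**Conclusion.** The point holds as a narrow gap in a stated safety rule. A persistent very high home diastolic with systolic between 100 and 180 prompts no immediate call. It normally leads only to a systolic-driven step about 7 days later, or up to 14, which may involve no clinician.

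The number affected cannot be derived from the protocol and is probably small, within about 17 participants and 100 measurement weeks. The existence of the gap follows from the text alone. The percentages rest on assumed SDs and independent readings and serve only to show that the systolic alert does not cover the case and what a diastolic alert might cost.

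A reader might infer that the pilot's conclusions are at risk. They are not: the recruitment and retention criteria do not depend on this rule. It is a cheap safety improvement that should be made.

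**What to change.** In 7.1.1 and on the instruction sheet, define the very-high alert as systolic >180 mmHg or diastolic above a stated limit, persisting after a repeat set of three measurements, and prompting a call to clinic staff for advice. Add no automatic diastolic titration step, and leave the entry criteria and the systolic target as they are.

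The limit is the sponsor's clinical decision. At SD 8 and mean home diastolic 90, a limit of 110 mmHg brings calls in up to about 8% of measurement weeks. A limit of 100 matches the figure in 5.2 but brings calls in about 15–79%. The cost is one line in each document plus those calls, and each call leads to advice rather than escalation by rule.
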